6.4 STUDY INTERVENTION COMPLIANCE

- Investigator or his/her delegate must ensure that IMP is administered to each participant according to the labeling instructions.
- IMPs accountability:
 - Intervention units are returned by the participant at each visit. In case of Direct to Patient process, the intervention units can be returned by the carrier (if defined in the contract).

- The Investigator or his/her delegate counts the number of remaining kits/pre-filled syringes and fills in the Intervention Log Form.
- The Investigator or his/her delegate records the dosing information on the appropriate pages of the electronic case report form (eCRF).
- The monitor in charge of the study then checks the eCRF data by comparing them with the IMP which he/she has retrieved and intervention log forms.

When participants are dosed at the site, they will receive study intervention directly from the Investigator or designee, under medical supervision. The date and time of each dose administered in the clinic will be recorded in the source documents and recorded in the eCRF. The dose of study intervention and study participant identification will be confirmed at the time of dosing by a member of the study site staff other than the person administering the study intervention.

When participants self-administer study intervention(s) at home, compliance with study intervention will be assessed at each visit. Compliance will be assessed by checking e-diary and used/unused kits/pre-filled syringes during the site visits and documented in the source documents and eCRF. Changes from the prescribed dosage regimen should be recorded in the eCRF.

Detailed instructions for transport, storage, preparation, and administration of IMP are provided to the participant. For doses not given at the study site participants will complete a dosing diary to document compliance with self-injection (or caregiver) of IMP, location of injection, and any symptoms. The diary will be kept as source data in the participant's study file

A record of the number of kits/pre-filled syringes dispensed to and taken by each participant must be maintained and reconciled with study intervention and compliance records. Intervention start and stop dates, including dates for intervention delays and/or dose reductions will also be recorded in the eCRF.

6.5 CONCOMITANT THERAPY

Any medication or vaccine (including over-the-counter or prescription medicines, vitamins, and/or herbal supplements) or other specific categories of interest that the participant is receiving at the time of screening or receives during the study must be recorded along with:

- Reason for use.
- Dates of administration including start and end dates.
- Dosage information including dose and frequency.

The Sponsor/Sponsor representative should be contacted if there are any questions regarding concomitant or prior therapy.

6.5.1 Background treatments

Participants that are using background INCS must have a stable dose regimen for at least 1 month at the time of V1. From the time of screening throughout the study treatment period, they should not change their background medications.

Intranasal corticosteroids other than nasal spray such as, drops, stents, or devices are not allowed as background treatment.

6.5.2 Prohibited medications

The following concomitant treatments are not permitted during the screening period and the study treatment period:

- Intravenous immunoglobulin (IVIG) therapy.
- Any systemic immunosuppressive treatment, such as methotrexate, cyclosporine, mycophenolate, tacrolimus, etc.
- Initiation of allergen immunotherapy.
- Intranasal corticosteroid drops; intranasal steroid emitting devices/stents; nasal spray using Exhalation Delivery System such as Xhance.
- All forms of systemic steroids are prohibited during screening and study treatment period except that a short term (<2 weeks) oral corticosteroids are allowed only in study treatment period as rescue medication (see rescue medication in [Section 6.5.3](#)).
- Live, attenuated vaccines.
- Other monoclonal antibodies (biological immunomodulators), including but not limited to anti-IgE, anti-IL-5 and anti-TNF, etc.
- Systemic antifungals and antibiotics are prohibited during screening and study treatment period except for rescue use (see rescue medication in [Section 6.5.3](#)).

Permitted concomitant medication

The following treatments are allowed:

- Intranasal normal saline.
- Short-acting β 2-adrenergic receptor agonists (SABA), long-acting β 2-adrenergic receptor agonists (LABA), and long-acting muscarinic acetylcholine receptor antagonists (LAMA).
- Methylxanthines (eg, theophylline, aminophyllines).
- Inhaled corticosteroids.
- Systemic antihistamines.
- Leukotriene antagonists/modifiers are permitted during the study, only for participants who were on a continuous treatment for \geq 30 days prior to Visit 1.
- Allergen immunotherapy in place for \geq 3 months prior to Visit 1 is permitted and the dose should be kept stable during screening and study treatment period.

- Single dose of topical decongestants administration for example oxymetazoline hydrochloride (to reduce the swelling and widen the path for the endoscope), as well as a topical anesthetic for example lidocaine are allowed before nasal brushing or before endoscopy.
- Other concomitant medication may be considered on a case-by-case basis by the Investigator in consultation with the Sponsor/Sponsor representative if required.

6.5.3 Rescue medicine

During the study treatment and follow-up periods, based on clinical evaluation, in case of worsening of signs and/or symptoms requiring medical intervention, the Investigator may consider rescue treatment with:

- Systemic antibiotics (up to 2 weeks) in case of acute infection.
- Short term courses (prednisone or prednisolone up to 2 weeks) of oral corticosteroids for AFRS or short courses of oral corticosteroids to treat other serious coexisting diseases (such as asthma exacerbation).
- Short term (\leq 4 weeks) systemic antifungal treatment based on participant's tolerability.
- Intranasal corticosteroids spray (initiation of INCS spray or change in dosing of a background INCS spray during the study period).
- Sino-nasal surgery for AFRS (8 weeks of IMP treatment is recommended prior to surgery to allow onset of treatment effect). For participants who undergo or are planned for surgery for AFRS, the Investigator may decide to continue IMP up to the time of surgery or end of treatment whichever date comes first. At the time of surgery, the participants will be permanently discontinued from study treatment.

Note: It is recommended if a participant must use SCS as per the Investigator's decision, the site should make every effort to perform clinical assessments (including an endoscopy, if it is needed) before starting treatment with SCS. If a participant needs to have CT scan around the time of surgery the next scheduled CT scan per protocol does not need to occur after surgery for AFRS. In any case, participants may not have more than 3 CT scans during the study. All this information collected will be recorded in dedicated eCRF pages.

6.6 DOSE MODIFICATION

No IMP dose modification is allowed. This is also applicable for adolescent participants who become adult during the study or participants who change weight band during the study.

6.7 INTERVENTION AFTER THE END OF THE STUDY

Sponsor will not be responsible for intervention after the EOS Visit. Intervention after the EOS Visit will be at the discretion of the Investigator or treating physician.

7 DISCONTINUATION OF STUDY INTERVENTION AND PARTICIPANT DISCONTINUATION/WITHDRAWAL

7.1 DISCONTINUATION OF STUDY INTERVENTION

7.1.1 Definitive discontinuation

In rare instances, it may be necessary for a participant to permanently discontinue (definitive discontinuation) study intervention. If study intervention is definitively discontinued, the participant will remain in the study to be evaluated for safety and efficacy. See the SoA ([Section 1.3](#)) for data to be collected at the time of discontinuation of study intervention and follow-up and for any further evaluations that need to be completed.

The Participants may withdraw from treatment with the IMP if they decide to do so, at any time and irrespective of the reason, or this may be the Investigator's decision. All efforts should be made to document the reasons for treatment discontinuation, and this should be documented in the eCRF.

Participants must be withdrawn from the study treatment (ie, from any further IMP) for the following reasons:

- At their own request or at the request of their legally authorized representative (legally authorized representative means an individual or judicial or other body authorized under applicable law to consent on behalf of a prospective participant to the participant's involvement in the procedure(s) involved in the research).
- If, in the Investigator's opinion, continuation in the study would be detrimental to the participant's well-being.
- At the specific request of the Sponsor.
- If they are treated with the specific prohibited medications mentioned in [Section 6.5.2](#).
- Sino-nasal surgery.
- If they miss 2 consecutive IMP doses.
- In the event of a protocol deviation, at the discretion of the Investigator or the Sponsor.
- Any code broken at the request of the Investigator.
- Pregnancy.
- Anaphylactic reactions or systemic allergic reactions that are related to IMP and require treatment (see [Section 10.9](#)).
- Diagnosis of a malignancy during study, excluding carcinoma in situ of the cervix, or squamous or basal cell carcinoma of the skin.
- Any opportunistic infection or other infections whose nature or course may suggest an immunocompromised status (see [Section 10.10](#)).

- Serum alanine aminotransferase (ALT) >3 upper limit of normal (ULN) and Total Bilirubin >2 ULN (see [Section 10.6](#)).
- Serum ALT >5 ULN if baseline ALT ≤ 2 ULN or ALT >8 ULN if baseline ALT >2 ULN (see [Section 10.6](#)).

Any abnormal laboratory value will be immediately rechecked for confirmation within a reasonable timeframe as assessed by the Investigator before making a decision of definitive discontinuation of the IMP for the concerned participant.

Handling of participants after definitive intervention discontinuation

If participants no longer wish to take the IMP, they will be encouraged to remain in the study.

The Investigators should discuss with them key visits to attend. The value of all their study data collected during their continued involvement will be emphasized as important to the public health value of the study.

Participants who withdraw from the study intervention should be explicitly asked about the contribution of possible AEs to their decision, and any AE information elicited must be documented.

Participants will be followed-up according to the study procedures specified in this protocol up to the scheduled date of study completion, or up to recovery or stabilization of any AE to be followed-up as specified in this protocol, whichever comes last.

Participants who discontinue the study intervention prematurely (prior to completing the 52-week treatment period) will perform, as soon as possible, the early termination visit with all assessments normally planned for the end of treatment (EOT) Visit (Visit 7) (refer [Section 8.1.1](#)) including a pharmacokinetics sample, if appropriate, to assure a complete clinical assessment in close temporal proximity to the premature termination of study treatment is available.

In addition, and to allow assessment of participant outcomes over the stipulated study period, participants will be asked and encouraged to complete all remaining study treatment visits, and participate in all assessments according to the visit schedule with a ± 3 day window. Under exceptional circumstances when a participant cannot come to the site for a scheduled visit, a phone contact can be made. During the phone contact, at least information about AEs, concomitant medication, and status of AFRS should be collected.

All cases of definitive intervention discontinuation must be recorded by the Investigator in the appropriate pages of the eCRF when considered as confirmed.

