7.1.2 Temporary discontinuation

Temporary intervention discontinuation may be considered by the Investigator because of suspected AEs. For all temporary intervention discontinuations, duration should be recorded by the Investigator in the appropriate pages of the eCRF.

Temporary intervention discontinuation decided by the Investigator corresponds to at least 1 dose not administered to the participant. Following a temporary interruption or missed dose, the treatment should be reinitiated at the next scheduled administration, maintaining the planned dose.

If 2 consecutive IMP doses have been missed, the study treatment will be definitively discontinued (see [Section 7.1.1](#)). Investigator must contact the participant to instruct not to take any subsequent injection.

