7.1.2.1 Rechallenge

Reinitiation of intervention with the IMP will be done under close and appropriate clinical/and or laboratory monitoring once the Investigator will have considered according to his/her best medical judgment that the responsibility of the IMP(s) in the occurrence of the concerned event was unlikely and if the selection criteria for the study are still met (refer to [Section 5](#)).

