Other screening tests	Highly sensitive serum (at screening) or urine (at other time points) hCG pregnancy test (as needed for WOCBP) ^e . Serology ^f : HBsAg, HBCAb total, HCVAb, HIV screen (Anti-HIV-1 and HIV-2 antibodies); Tuberculosis test (performed locally if required). All study-required laboratory assessments will be performed by a central laboratory, with the exception of TB test, urine pregnancy test, and routine urinalysis.

NOTES:

- a Details of liver chemistry stopping criteria with suggested actions and follow-up assessments related to liver monitoring are given in [Section 7.1](#) and [Section 10.6](#). All events which may indicate severe liver injury (possible Hy's Law, ALT or AST >3 × ULN and total bilirubin >2 × ULN) must be reported as an SAE.
- b All drug-induced liver injury (DILI) testing should be performed locally, unless there is no local support available in which case the analysis can be done at the central laboratory.
- c China will use urine sample (not dipstick).
- d In case the urine dipstick test result is abnormal, a urine sample should be sent into the central laboratory for microscopic examination.
- e After screening local urine testing will be standard for the protocol unless serum testing is required by local regulation or IRB/IEC.
- f In case of results showing HBsAg (negative), and HBCAb total (positive), an HBV DNA testing will be performed and confirmed negative prior to randomization. In case of results showing HCVAb (positive), an HCV RNA testing will be performed and should be confirmed negative prior to randomization.

For children aged ≥6 to <12 years, laboratory assessments are based on the child's weight and are detailed in the laboratory manual.

Investigators must document their review of each laboratory safety report.

Laboratory/analyte results that could unblind the study will not be reported to investigative sites or other blinded personnel until the study has been unblinded.

10.3 APPENDIX 3: ADVERSE EVENTS: DEFINITIONS AND PROCEDURES FOR RECORDING, EVALUATING, FOLLOW-UP, AND REPORTING

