Analyses according to PCSA will be performed based on the worst value during the treatment-emergent period, using all measurements (either local or central, either scheduled, nonscheduled or repeated).

For laboratory variables and vital signs above, the incidence of participants with at least one PCSA during the treatment-emergent period will be summarized regardless of the baseline level and according to the following baseline status categories:

- Normal/missing
- Abnormal according to PCSA criterion or criteria

Additional analyses for drug-induced liver injury

The following additional analyses will be performed for potential drug-induced liver injury:

- Time to onset of the initial alanine aminotransferase (ALT) or aspartate aminotransferase (AST) elevation ($>3 \times \text{ULN}$) and total bilirubin elevation ($>2 \times \text{ULN}$) during the treatment-emergent period will be analyzed using Kaplan-Meier method.
- A graph of the distribution of peak values of ALT versus peak values of total bilirubin during the treatment-emergent period will be provided.
- For each liver function test (eg, ALT), participants having experienced a PCSA (eg, ALT $>5 \text{ ULN}$) will be summarized using the following categories: Returned to baseline PCSA status (or returned to value $\leq \text{ULN}$ in case of missing baseline) before last IMP dose, Returned to baseline PCSA status after last IMP dose, Never returned to baseline PCSA status, No assessment after elevation. This summary will be performed by categories of elevation (ALT $>3, >5, >10, >20 \text{ ULN}$).

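### The combined liver stopping criterion in Protocol 7.1.1 names ALT only, although Table 9 note a puts ALT-led and AST-led cases in one possible Hy's Law category; a low-severity wording alignment

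*Protocol*

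**What the plan says.** Protocol 7.1.1 gives two laboratory liver criteria in the list of mandatory reasons for withdrawal from study treatment. The combined one is "Serum alanine aminotransferase (ALT) >3 upper limit of normal (ULN) and Total Bilirubin >2 ULN", with a reference to Section 10.6. The other is ALT alone: above 5 ULN if baseline ALT is at most 2 ULN, or above 8 ULN if baseline is higher. Before the decision to stop, "Any abnormal laboratory value will be immediately rechecked for confirmation within a reasonable timeframe as assessed by the Investigator".

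Note a to Table 9 (Protocol 10.2) begins: "Details of liver chemistry stopping criteria with suggested actions and follow-up assessments related to liver monitoring are given in" Sections 7.1 and 10.6. It then says that events which may indicate severe liver injury, defined as "ALT or AST >3 × ULN and total bilirubin >2 × ULN", must be reported as SAEs.

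Protocol 10.6 is headed for an increase in ALT. Its flow chart is not shown in the text available.

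The SAP (3.6.3.1, drug-induced liver injury) plans three items. The first is "Time to onset of the initial alanine aminotransferase (ALT) or aspartate aminotransferase (AST) elevation" above 3 × ULN and total bilirubin elevation above 2 × ULN.

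**The concern.** The protocol puts ALT-led and AST-led cases in the same possible Hy's Law category for reporting, and in the same note sends the reader to 7.1 for the stopping criteria. There, only the ALT-led case is named. No reason is given for the difference.

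What is at stake is the handling of an individual participant. For an ALT-led case, the site has a rule. For an AST-led case, it has to decide under general provisions. SAE reporting informs the sponsor but does not itself stop dosing, and Protocol 9.6 plans no data monitoring committee. An explicit laboratory criterion exists so that the stop does not depend on case-by-case judgement, and that reasoning applies equally to the AST-led case.

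**Working it through.** There is no planned figure to reproduce. The check compares the texts and then asks which rules an AST-led case meets.

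**Step 1: the texts side by side**

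| Place | Purpose | Enzyme | Thresholds |
|---|---|---|---|
| Protocol 7.1.1, combined bullet | Mandatory stop | ALT | >3 ULN with bilirubin >2 ULN |
| Protocol 7.1.1, second bullet | Mandatory stop | ALT | >5 ULN, or >8 ULN if baseline >2 ULN |
| Protocol 10.2, Table 9 note a | Mandatory SAE | ALT or AST | >3 × ULN with bilirubin >2 × ULN |
| Protocol 10.3.2 | Illustrative list of medically important events | ALT | >3 × ULN with bilirubin >2 × ULN, or ALT alone >10 × ULN |
| Protocol 8.3.6 and SAP Table 6 | AESI | ALT | >5 × ULN, or >8 × ULN if baseline >2 × ULN |
| SAP 3.6.3.1, first liver item | Descriptive time to onset | ALT or AST | >3 × ULN and bilirubin >2 × ULN |

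Between the combined bullet and note a, the thresholds agree. Only the enzyme differs.

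**Step 2: apply the rules to each case, all with bilirubin above 2 × ULN**

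| Case | SAE under note a | Combined bullet of 7.1.1 | ALT-alone bullet of 7.1.1 |
|---|---|---|---|
| ALT >3, AST ≤3 | Yes | Met | Only if ALT exceeds 5 or 8 |
| ALT >3, AST >3 | Yes | Met | Only if ALT exceeds 5 or 8 |
| ALT ≤3, AST >3 | Yes | Not met | Cannot be met, since 3 < 5 < 8 |

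The third row is the gap.

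**Step 3: other routes to a stop for the third row**

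- Protocol 7.1.1 also requires withdrawal if the investigator considers continuation harmful to the participant, or if the sponsor asks for it. Under 8.3.1 the SAE reaches the sponsor within 24 hours. Both routes rest on judgement.
- Under 7.1.2 the investigator may hold doses. "If 2 consecutive IMP doses have been missed, the study treatment will be definitively discontinued", so the stop becomes mandatory at the second missed dose: 2 × 14 = 28 days after the last dose given for q2w, 2 × 28 = 56 days for q4w. No drug is given in between, but this requires a decision to hold both doses.
- After one held dose, 7.1.2 says "the treatment should be reinitiated at the next scheduled administration, maintaining the planned dose". Under 7.1.2.1 a restart needs the investigator to consider that "the responsibility of the IMP(s) in the occurrence of the concerned event was unlikely", close monitoring, and selection criteria that are still met.

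**Step 4: when the rule could act**

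The schedule of activities (Protocol 1.3) places chemistry after Day 1 at Weeks 12, 24, 52 and 64. The last dose is at Week 50 (q2w) or Week 48 (q4w). Weeks 52 and 64 come after both, so scheduled results can change dosing only at Weeks 12 and 24. Unscheduled tests could add occasions.

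**Step 5: frequency**

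The documents give no rate for AST-led possible Hy's Law cases. Protocol 2.3.2 reports 8720 participants exposed to dupilumab, and its list of identified adverse drug reactions contains no hepatic reaction. That list is not a case count, so it cannot be turned into a rate, but it is consistent with the event being rare.

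**The case against.** The strongest objection is that half of the stopping rule cannot be seen. The bullet refers to 10.6, note a names 7.1 and 10.6 together, and the 10.6 chart is missing only because figures were not reproduced. A reader might infer that the protocol has no AST stopping rule at all. The documents do not support that, because the chart may contain an AST branch. This objection stands, and it makes the point conditional. If 10.6 does cover AST, the bullet in 7.1.1 should still match it.

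Second, ALT-led action runs through the plan (7.1.1, 8.3.6, 10.3.2, the heading of 10.6, SAP Table 6). A wider net for reporting than for withdrawal is defensible, and AST can rise for non-hepatic reasons. This stands as far as there being no outright contradiction: the texts serve different purposes. It carries less weight against the change itself, because the combined criterion still requires bilirubin above 2 ULN and the value is rechecked before stopping.

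Third, a reader might infer that the SAP liver analysis as a whole uses ALT or AST. It does not. Of its three items only the first names AST, and that item could be read as separate onset times for the aminotransferase and for bilirubin. The second plots peak ALT against peak bilirubin. The third covers each liver function test, with ALT as its example. All are descriptive and none governs dosing, so the SAP is supporting context only.

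Fourth, a reader might infer that an AST-led case would simply be put back on drug after one held dose. The restart conditions in 7.1.2.1 and the judgement-based stops in 7.1.1 do not support that.

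**Conclusion.** The point holds in a limited form. On the wording of 7.1.1, an AST-led possible Hy's Law case with ALT at or below 3 × ULN is a mandatory SAE that meets no laboratory stopping criterion. Withdrawal then depends on the judgement of the investigator or sponsor. The conclusion assumes that the 10.6 chart has no AST branch, which could not be checked.

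It is a cheap improvement of low severity. It concerns a rare case in a trial of about 62 participants. One might be tempted to attach an expected number of cases or a probability of at least one, but any such figure would rest on an assumed rate with no source in the documents, so none is given. There is no effect on power, alpha or the primary analysis.

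**What to change.** Change the combined bullet in Protocol 7.1.1 to: *Serum ALT or AST >3 ULN and Total Bilirubin >2 ULN (see Section 10.6)*. Check the 10.6 flow chart and make it agree. The ALT-alone bullet, the baseline note in 10.6 and the illustrative list in 10.3.2 can stay as they are.

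AST, bilirubin and creatine phosphokinase are already in the Table 9 panel, so no test or visit is added. The edit needs IRB/IEC approval under Protocol 10.1.1. It does not justify an amendment of its own and can go into the next one, if there is one. It helps only while participants are still being dosed.

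The downside is a rare stop for a non-hepatic AST rise with coincident raised bilirubin. The recheck in 7.1.1 limits this, and creatine phosphokinase helps to recognise a muscle source.
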